## Specific Aim 2 -

To determine the safety of oral L-citrulline supplementation in premature infants. Increased production of NO may lead to systemic hypotension by its vasodilator effect. All infants in the neonatal ICU are always on electronic monitors and monitored for heart rate, oxygen saturations and BP. We will continuously monitor all infants for systemic hypotension. Significant hypotension will be defined as a 25% drop in systemic mean blood pressure (measure by non-invasive blood pressure monitoring). Other parameters to be recorded include increase in oxygen requirements/escalation in respiratory support, metabolic abnormalities (on routine glucoses and electrolyte monitoring), effect on bone-marrow by weekly complete blood counts (done routinely on preterm infants).

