### 4.0 Treatment Assignment/Randomization

**Recruitment** - Parents of all eligible infants will be approached by research investigator to discuss about the study & research protocol in detail. All questions & concerns will be answered in very simple language & parents will be given written consent form to read. Within 24 to 48 hours, the parents will be approached again to discuss & explain any question they have. We expect around 70 - 75% success in the recruitment. Every year, we deliver around 50 infants ( $\leq$ 30 weeks' gestation). We hope to recruit our desired sample of 42 infants (14 in each study group) within 12 months.

**Sample size:** 14 preterm infants will be randomized to each group (total sample 42) A sample size of 14 at each group (low, median, and high dose) for efficacy endpoint will reach a power of 0.80 to detect an effect size of 0.5 based on one-way ANOVA with a 0.05 significance level. A sample size of 11 at each group for safety endpoint will reach a power of 0.92 at a 0.05 significant level for an equivalence test of means using two onesided tests, when the true difference between the means is 0.0 mmHg, the standard deviation is 10.0 mmHg, and the equivalence limits are -15.0 mm Hg and 15.0 mmHg.

**Randomization:** Adaptive randomization method will be used – each new participant will be sequentially assigned to a particular treatment group by taking into account the previous assignments of participants. For example, first recruit will be Group 1, second Group 2, third Group 3, fourth Group 1 and so on. The study will be blinded to the nurses and parents. If patients complete 12/14 doses of the treatment, they will be analyzed in the treatment arm.

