# Assessment of Subject Compliance with Study Intervention/Investigational Product

Since all doses will directly be administered by the bedside nurse, non-compliance is not applicable to this study. Subjects must receive 12/14 doses to be considered a complete subject.

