## 7.0 Adverse Events or Unanticipated Problems involving Risk to Participants or Others

Immediate risks: Increased NO production may theoretically lead to systemic hypotension – all these infants will be in an intensive care setting with cardiac monitors and continuous blood pressure monitoring. Significant hypotension will be defined as a 25% drop in systemic mean blood pressure from baseline (average mean arterial pressure in the week prior to starting study drug).

Local irritation to skin or eyes is possible with direct contact with study drug.

Long-range risks: A theoretical risk of adverse impact on structural remodeling of pulmonary architecture vis increase in arginase two expression in lungs (seen in rats).

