- Severe: events interrupt a patient's usual daily activity and may require systemic drug therapy or other treatment. Severe events are usually incapacitating.
- Life threatening: any adverse drug experience that places the patient or subject, in the view of the investigator, at immediate risk of death from the reaction as it occurred, i.e., it does not include a reaction that had it occurred in a more severe form, might have caused death.

Changes in the severity of an AE should be documented to allow an assessment of the duration of the event at each level of intensity to be performed. Adverse events characterized as intermittent require documentation of onset and duration of each episode.

Protocol Grading System for Hypotension:

Mild: Drop in systemic mean arterial pressure (MAP)  $\leq$  10% from baseline

Moderate: Drop in systemic mean arterial pressure (MAP)  $\leq$  25% from baseline

Severe: Drop in mean arterial pressure (MAP) > 25% from baseline

Life threatening: Severe hypotension requiring 2 or more inotropes (Dopamine, Epinephrine, Norepinephrine)

**Relationship to Study Products:** If there is any doubt as to whether a clinical observation is an AE, the event will be reported. All AEs must have their relationship to study product assessed using the terms: associated or not associated. In a clinical trial, the study product must always be suspect. To help assess, the following guidelines are used.

- Associated The event is temporally related to the administration of the study product and no other etiology explains the event.
- Not Associated The event is temporally independent of study product and/or the event appears to be explained by another etiology.

**Serious Adverse Event (SAE)**: An SAE in our study will be defined as an AE that meets one of the following conditions:

- Death during the period of protocol defined surveillance
- Life-threatening event (defined as a subject at immediate risk of death at the time of the event) significant hypotension requiring 2 or more inotropes

- Results in a persistent or significant disability/incapacity: Intraventricular hemorrhage Grade III or more, Necrotizing enterocolitis requiring surgery, Retinopathy of prematurity requiring surgery
- Significant lab abnormalities: Thrombocytopenia < 50,000

All SAEs will be:

- recorded on the appropriate SAE CRF
- followed through resolution by a study clinician
- reviewed and evaluated by a study clinician

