## 8.0 Study Withdrawal/Discontinuation

### **Reasons for Withdrawal**

A study subject will be discontinued from participation in the study if any of the following occur:

- Unacceptable toxicity or adverse event (AE): Drop in systemic mean blood pressure > 25% from baseline
- Unacceptable laboratory abnormalities: Thrombocytopenia < 50,000 not explained by other co-existing conditions
- Intercurrent illness, or other medical condition or situation occurs such that continued participation in the study would not be in the best interest of the subject in the opinion of the treating investigator, for e.g. necrotizing enterocolitis requiring subject to be made NPO.
- Development of any exclusion criteria
- Parents withdraw consent to continue in the research for any reason

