### Handling of Withdrawals

Any subjects that withdraw from the study will continue to receive standard of care treatment according to our NICU protocols and will continue to be followed clinically by the primary neonatologist. Safety data from these subjects will be presented to the DSMB for evaluation.

Since this is a pilot study, we will not need to replace subjects in case of withdrawals.

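### The only safety power figure (TOST, ±15 mmHg, 0.92) names neither the means nor the pressure compared, and on neither plausible reading does it support a within-infant test of whether supplementation lowers blood pressure

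*Combined protocol and SAP*

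**What the plan says.** Specific Aim 2 gives the safety question and its mechanism: "Increased production of NO may lead to systemic hypotension by its vasodilator effect". Hypotension is defined within the infant throughout. Section 7.0 measures the drop "from baseline (average mean arterial pressure in the week prior to starting study drug"). Its grading system has "Severe: Drop in mean arterial pressure (MAP) > 25% from baseline", and section 8.0 discontinues an infant for "Drop in systemic mean blood pressure > 25% from baseline".

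The only power statement for safety is in section 4.0, under sample size. It is a TOST comparison of means at the 0.05 level with 11 infants per group, an assumed true difference of 0 and power 0.92, in which "the standard deviation is 10.0 mmHg, and the equivalence limits are -15.0 mm Hg and 15.0 mmHg". The planned enrolment of 14 per group comes from the efficacy calculation. All three groups receive L-citrulline.

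Section 9.0 lists safety as a secondary outcome and repeats only the efficacy sample size. It names linear models, repeated-measures ANOVA and logistic modelling without attaching them to endpoints. It applies one-way ANOVA to plasma arginine and citrulline and urinary nitrite and nitrate, and then mentions a paired t-test of values before and after treatment.

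On who is analysed, section 4.0 states "If patients complete 12/14 doses of the treatment, they will be analyzed in the treatment arm", and the compliance paragraph of section 6.0 states "Subjects must receive 12/14 doses to be considered a complete subject". Section 9.0 excludes infants who lack a blood sample for arginine or citrulline, and also declares an intention-to-treat approach. For withdrawn infants, section 8.0 says "Safety data from these subjects will be presented to the DSMB for evaluation".

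**The concern.** Aim 2 asks whether the drug lowers an infant's blood pressure. The one calculation offered for that endpoint does not say what is compared with what. Without an untreated arm, a comparison among active doses says nothing about an effect that all doses share. A passed equivalence test could nevertheless be read as evidence of safety.

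The statistics section does not settle the matter, because no named method is assigned to blood pressure and the TOST does not reappear. In the visible text the 12-of-14-dose rule and the blood-sample exclusion are not confined to the efficacy analysis. The infants who say most about hypotension are those withdrawn for it, and they are the ones these rules could remove. The background section says the pilot will inform a later placebo-controlled trial. That trial would need a within-infant estimate of blood-pressure change and an honest statement of its precision.

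**Working it through.** **Inputs from section 4.0:** n = 11 per group (14 planned), SD 10 mmHg, margin 15 mmHg, true difference 0, α = 0.05 for each one-sided test.

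**1. Reproducing 0.92.** For two independent groups, SE = 10·√(2/11) = 4.264 mmHg and t(0.95, 20) = 1.725. Equivalence is declared when |difference| + t·SE (with SE estimated from the data) is below 15. Integrating over the distribution of the pooled SD gives power 0.920, so the stated figure is right for this test. With n = 14 it is 0.973.

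**2. Dose versus dose.** If every dose lowers the mean by the same amount f, then (μ₁ − f) − (μ₂ − f) = μ₁ − μ₂. The fall cancels, and the pass probability does not depend on f. Simulated common falls of 0, 5, 10, 15 and 20 mmHg all gave 0.92 (n = 11) and 0.97 (n = 14). With equal means, all three pairs pass together with probability 0.81 (n = 11) or 0.93 (n = 14). The test does respond when doses differ:

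| True difference between doses (mmHg) | Pass probability, n = 11 | n = 14 |
|---|---|---|
| 0 | 0.92 | 0.97 |
| 5 | 0.73 | 0.82 |
| 10 | 0.30 | 0.36 |
| 15 | 0.05 | 0.05 |

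**3. Before versus after.** Treating the two sets of readings as unpaired gives the same 0.920. For a paired test with SD 10 per reading and correlation ρ, the SD of change is 10·√(2(1 − ρ)), SE = SD of change/√11, and t(0.95, 10) = 1.812. The documents give no ρ, so a range is shown:

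| ρ | SD of change (mmHg) | Power, n = 11 |
|---|---|---|
| 0 | 14.1 | 0.895 |
| 0.1 | 13.4 | 0.928 |
| 0.3 | 11.8 | 0.976 |
| 0.5 | 10.0 | 0.997 |

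A paired test gives about 0.92 only if an infant's two readings are almost uncorrelated. If the 10 mmHg was meant as the SD of change, power would be 0.997, not 0.92.

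**4. Margin.** A 15 mmHg fall equals 25% only at a baseline of 15/0.25 = 60 mmHg. The documents give no baseline MAP. For assumed baselines of 30 to 60 mmHg, the margin is a fall of 15/30 = 50% down to 15/60 = 25%.

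**5. Analysis set.** An infant withdrawn for a fall above 25% before the twelfth dose fails the 12-of-14 rule. An infant withdrawn before the Day 7 sample may also lack that sample. Nothing visible exempts blood pressure from either rule.

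**6. What the design can deliver.** With no events, the exact two-sided 95% upper limit is 1 − 0.025^(1/n). This is 1 − 0.025^(1/14) = 0.232 per dose and 1 − 0.025^(1/42) = 0.084 pooled. One event in 14 gives 0.2% to 34%. For mean percent change, the 95% half-width is t(0.975, n − 1)·SD/√n. At assumed SDs of 10, 15 and 20 percentage points (not in the documents) it is 5.8, 8.7 and 11.5 points for n = 14, and 3.1, 4.7 and 6.2 points for n = 42.

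**The case against.** The strongest reply is that dose versus dose is not established. A per-group sample size also fits a before/after comparison within each dose group, and every blood-pressure definition in the protocol is a change from the infant's own baseline. This stands: a reader might infer that the powered test certainly cannot see a drug effect, and the documents do not support that certainty. It does not rescue the calculation, because on the before/after reading 0.92 does not describe a within-infant test unless the readings are almost uncorrelated.

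A reader might also infer that no within-infant analysis is planned. That goes too far. Section 9.0 has a paired t-test and lists repeated-measures ANOVA, and neither is expressly restricted to laboratory values. What holds is that neither is tied to blood pressure.

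A third tempting inference is that infants with hypotension will be excluded. No text says so. Section 9.0 declares intention-to-treat, the blood-sample rule seems aimed at the laboratory analyses, and safety data on withdrawn infants go to the DSMB. Board review does not define the final analysis set, however, so the gap remains.

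Finally, this is a pilot, safety is a secondary outcome, no decision rule uses the 0.92, and a comparison among doses is useful in dose-ranging. All of that is fair and limits the consequence. Monitoring, grading, withdrawal and DSMB review of individual infants are separate from the powered test and are not criticised here.

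**Conclusion.** The point holds as a specification fault with a practical consequence, and should be fixed. The 0.92 is arithmetically correct, but the comparison it describes is unstated. Read as dose versus dose, it passes each pair with probability 0.92 (n = 11) or 0.97 (n = 14) under any fall common to the doses, so it cannot address Aim 2. Read as before versus after, it does not match a within-infant test except at a correlation of about 0 to 0.1. The size of the problem therefore depends on which reading was intended, and the documents do not say.

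The loss of infants withdrawn for hypotension is conditional on the dose or blood-sample rule being applied to blood pressure. No justification of the 15 mmHg margin is visible. Part of section 7.0 was not available for this review, so the statements on the margin and the analysis set concern the visible text only. The point is limited to blood pressure.

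**What to change.** In section 4.0, either remove the TOST sentence as the basis for the safety endpoint, or keep it labelled as a dose-versus-dose comparison with the pressure variable and the means named and the margin justified.

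In section 9.0, pre-specify a within-infant analysis of percent change in MAP from the baseline already defined in section 7.0, and state which on-treatment value is used. Per dose and pooled, report:

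- the mean percent change with a two-sided 95% confidence interval;
- the number and proportion of infants with a fall above 25%, with an exact two-sided 95% interval.

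A dose-trend estimate is optional. Define the set as every infant given at least one dose, including those withdrawn, and state that neither the 12-of-14-dose rule nor the blood-sample exclusion applies to it. State the precision (upper limit 23% for 0/14 and 8.4% for 0/42), and that change from baseline is descriptive without an untreated arm.

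The cost is protocol wording. The 14 per group does not change, because it rests on the efficacy calculation. The stated safety precision will look less favourable than 0.92. Change from baseline will make a common fall visible but cannot separate drug effect from maturation or illness.

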## 3.0 Inclusion/Exclusion Criteria

Inclusion criteria - Subjects must meet all of the inclusion criteria in order to be eligible to participate in the study.

1. Infants  $\leq$  30 weeks' gestational age born at UTMB, Galveston.

2. Parents have provided informed consent/assent in a manner that is approved by the IRB

The reason for the inclusion of such a vulnerable population is that BPD is primarily a disease of premature infants and PH is a common complication of BPD. It is also a condition with high mortality and there still exists significant confusion over appropriate management. Being a randomized controlled trial, the study does add certain risks to the subjects: frequent blood draws (minimized by using discarded blood and urine samples) . Since diagnosis and management of BPD\_PH is not currently standard of practice, we will not be withholding any beneficial therapy. The present research protocol will not interfere in the management of the preterm infants as treating neonatal team will be taking all management decisions. All risks will be explained to the parents and written informed consent will be obtained from the parents of all subjects.

Exclusion criteria - Subjects meeting any of the exclusion criteria at baseline will be excluded from study participation.

1. Known congenital or chromosomal anomalies.

2. Congenital heart disease affecting cardio-respiratory system (other than PDA, PFO or ASD)

3. NEC, sepsis, or any condition requiring surgery prior to recruitment

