### 5.0 Study Procedures

**Data collection** - Antenatal, delivery & post-natal (after birth), all detailed data will be collected from electronic medical records (EMR) by the investigators & saved in a password protected computer. We will calculate SNAPPE 2 (Score for Neonatal Acute Physiology – Perinatal Extension 2 – a 9 point validated scoring system that predicts neonatal mortality(10)) for all subjects to ensure equal distribution of sick infants.

**Study drug** – Oral/enteral L-Citrulline as 10 % solution (100 mg/ml) will be provided to the bedside nurse by the Investigational Pediatric Pharmacy. The drug will be given via gavage feeding by bolus infusions followed by a 0.5 ml water flush twice daily (1200 and 0000). Bolus dosing will be needed due to the small volumes (0.5–1.5 ml per dose in most infants). The volume of nasogastric tubing used in preterm infants (Ameritus 4.0 Fr 50 cm) is 0.48 ml, therefore we will follow the administration with 0.5 ml of saline/water flush to ensure all the study drug is delivered to the patient.

Dispensing study drug - After enrollment & randomization, the research nurse will inform the pharmacy about randomization group. A 10% solution of L-citrulline will be prepared to administer 50 mg/kg, 100 mg/kg and 150 mg/kg doses for Groups 1,2 and 3 respectively. The shelf life of dispensed L-citrulline is 24 hours. L-citrulline will be dispensed as a single dose twice daily for each subject.

Administration of study drug - Will be given via gavage feeding tube twice daily (1200  $\pm$  30 mins, 0000  $\pm$  30 mins). The time of 0000 will be in the window of citrulline's peak serum levels at 5-8 hours when routine blood collection is done at 0400(11). L-citrulline will be given by the bedside nurse as a bolus followed by 0.5 ml water flush. L-citrulline will be given separate from feeds to avoid any confusion.

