### Rationale:

Children with urea cycle defects have been treated with L-citrulline for decades and showed no evidence of toxicity. Previous studies in literature have not reported any significant adverse effects. The benefit of treatment (helping treat or prevent BPD\_PH) far outweighs the risks since this condition is associated with significant morbidity/mortality and no preventative measures exist at this time. The study drug has already been tested on animal models and there are no alternatives to studying the safety, efficacy and dosing in preterm infants.

ICH E6 defines an AE as any untoward medical occurrence in a patient or clinical investigation subject administered a pharmaceutical product regardless of its causal relationship to the study treatment. An AE can therefore be any unfavorable and unintended sign (including an abnormal laboratory finding), symptom, or disease temporally associated with the use of medicinal (investigational) product.

All AEs including local and systemic reactions not meeting the criteria for "serious adverse events" should be captured on the appropriate CRF. Information to be collected includes event description, time of onset, clinician's assessment of severity, relationship to study product (assessed only by those with the training and authority to make a diagnosis, which would include MD, PA, Nurse Practitioner, DO, or DDS), and time of resolution/stabilization of the event. All AEs occurring while on study must be documented appropriately regardless of relationship. All AEs will be followed to adequate resolution.

Any medical condition that is present at the time that the patient is screened will be considered as baseline and will not be reported as an AE. However, if it deteriorates at any time during the study, it should be recorded as an AE.

All AEs must be graded for severity and relationship to study product.

**Severity of Event:** All AEs will be assessed by the clinician using a protocol defined grading system. For events not included in the protocol defined grading system, then the following guidelines will be used to quantify intensity.

- Mild: events require minimal or no treatment and do not interfere with the patient's daily activities.
- Moderate: events result in a low level of inconvenience or concern with the therapeutic measures. Moderate events may cause some interference with functioning.

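### The adaptive randomization is a fixed 1-2-3 rotation, so every dose assignment is known in advance; the claim that nurses are blinded is also unsupported

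*Combined protocol and SAP*

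**What the plan says.** Section 4.0 names the method adaptive randomization and says that each assignment takes earlier ones into account. The rule it then gives is "For example, first recruit will be Group 1, second Group 2, third Group 3, fourth Group 1 and so on". It states no probability, generator, block, stratum or covariate. The same section says that the 42 infants, 14 per group, are randomized, and section 3.0 explains the risks to a vulnerable population with the words "Being a randomized controlled trial".

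On handling the assignment, section 5.0 says that after enrolment "the research nurse will inform the pharmacy about randomization group". No central service, sealed envelope or pharmacy-held list is described. Section 5.0 also has SNAPPE-II calculated "for all subjects to ensure equal distribution of sick infants", but the score appears neither in the assignment rule nor in any analysis stated in section 9.0.

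On blinding, section 4.0 says "The study will be blinded to the nurses and parents". Section 5.0 says "A 10% solution of L-citrulline will be prepared to administer 50 mg/kg, 100 mg/kg and 150 mg/kg doses", and the bedside nurse gives the dose. Section 7.0 has the relationship of adverse events to study product "assessed only by those with the training and authority to make a diagnosis"; these clinicians are not covered by the blinding statement.

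Section 9.0 compares the three groups by one-way ANOVA and tests change within infants by paired t-test. Section 4.0 sizes the safety endpoint for an equivalence test of means.

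**The concern.** Randomization protects a comparison between groups only if the next assignment cannot be foreseen. Here it can. The investigator who approaches parents is not listed as blinded, and consent involves a second approach 24 to 48 hours after the first, so its order and timing can shift with the dose that is due next. A sicker or more stable infant could then be steered towards or away from a dose, deliberately or not. Objective assays do not protect against this, because the selection acts before any sample is taken.

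The exposed results are the between-dose ANOVA, the dose choice in Aim 3 where it compares groups, and any between-group safety comparison. Section 1.0 says that the findings will inform a later placebo-controlled trial.

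Blinding is a second, smaller matter. If the dose can be inferred at the bedside, or is known to the clinicians who grade events, then decisions on respiratory support and judgements of severity and relatedness may be influenced. The HPLC-MS and GC-MS measurements and the numeric blood-pressure cut-offs are not exposed in the same way.

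**Working it through.** **The plan's own figures.** Three groups of 14 (N = 42), effect size f = 0.5, alpha 0.05 (section 4.0). Noncentrality = N × f² = 42 × 0.25 = 10.5 on 2 and 39 degrees of freedom; power = 0.803 against the stated 0.80. Equivalence test with 11 per group, SD 10 mmHg, limits ±15 mmHg, two one-sided tests at 0.05: power = 0.920 against the stated 0.92. Both reproduce, so the concern does not rest on a wrong sample size.

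**Is there any random element?** The label says adaptive; the rule says 1, 2, 3, 1 and onward. Using previous assignments could describe minimization, but that needs named factors, and none is given. The rule yields one sequence. The number of possible sequences with 14 per group is 42!/(14!)³, about 2.1 × 10¹⁸.

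**Predictability of the next assignment** (share guessed correctly by an observer who sees all past assignments and always picks the group with most places left in the block)

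- Rotation: 42/42 = 100%.
- Blocks of 3: (1/3 + 1/2 + 1)/3 = 1.833/3 = 61.1%.
- Blocks of 6, with E(a,b,c) the expected correct guesses when a, b and c places remain:
  - E(1,1,1) = 1.833 and E(0,1,2) = 2/3 + (1/3)(2) + (2/3)(1.5) = 2.333
  - E(0,2,2) = 1/2 + 2.333 = 2.833
  - E(1,1,2) = 1/2 + (1/2)(1.833) + (1/2)(2.333) = 2.583
  - E(1,2,2) = 2/5 + (1/5)(2.833) + (4/5)(2.583) = 3.033
  - E(2,2,2) = 1/3 + 3.033 = 3.367, and 3.367/6 = 56.1%
- Six blocks of 3 and four of 6 (18 + 24 = 42): (6 × 1.833 + 4 × 3.367)/42 = 24.47/42 = 58.3%.
- Any of these lists with past assignments unseen: 1/3 = 33%.

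In 40,000 simulated lists of the mixed form, every one ended 14/14/14. Two groups can differ by at most 2 at any point, when the first two places in a block of 6 go to the same group. Drawing block sizes at random and cutting off at 42 gave exact balance in only 80% of lists.

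**Nurse blinding.** At 100 mg/ml, doses of 50, 100 and 150 mg/kg are 0.5, 1.0 and 1.5 ml/kg. Volume alone is ambiguous: 1.0 ml fits a 2 kg infant in Group 1 (2 × 0.5) or a 1 kg infant in Group 2 (1 × 1.0). With the weight it is not. The closest two doses differ by a ratio of 1.5/1.0 = 1.5, so a weight known to within a factor of √1.5 = 1.22 separates all three groups. That the bedside nurse knows the weight is an assumption; the protocol does not say so. The blinding statement also refers to nurses in general, although the research nurse must know the group in order to report it. Nothing shows that parents would be unblinded.

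**What a selection effect could do (illustration only).** The documents give no size for it, so a shift is assumed. Suppose there is no true dose effect, but selection shifts the outcome linearly by d within-group SDs from Group 1 to Group 3. Then f² = d²/6, the noncentrality is 42 × d²/6 = 7d², and the nominal 5% ANOVA rejects as follows:

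| d (SD) | 7d² | Rejection rate |
|---|---|---|
| 0.25 | 0.44 | 8% |
| 0.50 | 1.75 | 19% |
| 0.75 | 3.94 | 38% |
| 1.00 | 7.00 | 62% |

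**Room for steering.** Section 4.0 expects about 50 eligible births a year and 70 to 75% consent: 50 × 0.70 = 35 and 50 × 0.75 = 37.5 infants, against a target of 42. With all eligible parents to be approached, what remains open is mainly the order and timing of consent.

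**The case against.** This is a single-centre pilot with assayed primary outcomes, a paired analysis that does not depend on allocation, and little scope to pick and choose infants. No bias is shown. The sequence is introduced as an example, absence of concealment means only that none is described, and some pages of the protocol were not available. The blinding point needs a nurse who knows the weight, the concentration and the three dose levels, and masked syringes are not ruled out. SNAPPE-II could enter the unspecified linear models in section 9.0. On this view the defect is one of labelling and conduct.

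Much of this stands as a limit on the likely size of the problem. On blinding, the supportable statement is that no masking is described. Adjustment for SNAPPE-II is unspecified rather than excluded.

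It does not rescue the allocation. The example is continued indefinitely and no other rule appears. A sequence printed in the protocol with its starting group cannot be concealed by any step that missing pages might contain. Neither the assays nor the pilot status makes the three groups comparable, and comparing doses is what the study is for.

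**Conclusion.** The concern holds and must be fixed. The allocation as written is deterministic: 42 of 42 assignments are predictable, and the study is not randomized in the sense that sections 3.0 and 4.0 claim. The between-dose ANOVA and any between-group safety comparison are open to selection bias of unknown size; no actual bias is asserted. The paired pre-post test is much less affected. SNAPPE-II cannot deliver the balance claimed for it, since no stated step uses it.

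The nurse-blinding claim is unsupported rather than disproved. It fails if the bedside nurse knows the infant's weight roughly, which is assumed here. The clinicians who judge adverse events lie outside the claim altogether.

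**What to change.** 1. Replace the rotation in section 4.0 with a computer-generated 1:1:1 permuted-block list of varying, undisclosed block sizes that total 42, for example six blocks of 3 and four of 6 in shuffled order. Other concealed random lists would also serve; fixing the number of blocks keeps 14 per group.
2. Have the Investigational Pharmacy hold the list and apply the next assignment only after consent, when the infant qualifies to start study drug. Section 5.0 starts drug only once the infant has been off TPN for at least 3 days, so assigning at that point avoids using up places on infants who never start. Delete the step in which the research nurse tells the pharmacy the group.
3. Name SNAPPE-II as a covariate in the between-dose analysis, not as a stratum, so that the list stays balanced.
4. Delete the claim that nurses are blinded, or have the pharmacy mask the volume if it judges this feasible. Label assay samples without the group, and have severity and relatedness judged by a clinician who is not told it.
5. If the rotation is kept, describe the study as non-randomised with alternating allocation and reconcile sections 3.0, 4.0 and 5.0.

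The cost is minor wording, one generated list and list-keeping by the pharmacy. Volume masking would be extra pharmacy work and is optional. N stays 42 and the allocation change leaves the ANOVA power at 0.803. If recruitment stops early, any two groups differ by at most 2 infants as assigned.
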